1.0 Rationale and Specific Aims

The logistic advantages and advanced training capabilities of the G-EO System, as well as the benefits reported in other populations, support this strategy as a potentially potent rehabilitation tool for restoring and maintaining function in progressive MS. This approach represents a paradigm shifting opportunity for improving current clinical practices for patients with progressive MS. If successful, this project will provide initial evidence for increasing patient access to the G-EO System, and this could be accomplished through “regional technology centers” using a rural health-delivery approach.

There are several novel aspects of the proposed trial: (1) the examination of a novel gait rehabilitation stimulus (G-EO System) that could alter current clinical practices; (2) the focus on patients with progressive MS who have gait impairment (i.e., those who have received minimal research attention), which was recently described as the greatest therapeutic challenge facing the MS community; and (3) a study design that accounts for standard therapy.

Specific Aims: We propose a single-blinded, randomized pilot trial of electromechanically-assisted gait training using the G-EO System in patients with progressive MS with gait disability (EDSS=4.0-7.5).

Specific Aim 1 will establish the safety and feasibility of gait training using the G-EO System.

Specific Aim 2 will determine the efficacy of gait training using the G-EO System for improving mobility, symptomatic, quality of life, and participatory outcomes.

2.0 Inclusion/Exclusion Criteria

Inclusion criteria

- 18-64 years
- Confirmed diagnosis of PPMS or SPMS (this will be confirmed by the referring physician)
- EDSS 4.0-7.5²²
- Stable course of disease-modifying therapy over the past 6 months
- Asymptomatic (i.e., no underlying cardiovascular disease)
- Physician approval for exercise
- Willingness to visit the IU Health Neurosciences Center for testing and training

Exclusion criteria

- Pregnancy
- Current use of dalfampridine (Ampyra®)
- Conventional physical therapy or G-EO training within the past 6 months
- Height <1m or >2m
- Body weight >150 kg
- Contraindications to G-EO gait training (e.g., bone instability)

3.0 Enrollment/Randomization

National MS Society, , <http://nationalmssociety.org/for-professionals/researchers/index.aspx>

A convenience sample of 20 persons with progressive MS will be enrolled for this pilot clinical trial. Recruitment will occur through neurologists at the IU Health Neuroscience Center. Each participant will be given time to read the consent form or have it read to them and to ask questions (see Informed Consent Draft). Consent will be obtained before randomization and assessments. The consent process will take place at the Indiana Center for Advanced Neurorehabilitation (ICAN) in the Neurorehabilitation and Robotics IU Health Neuroscience Center, [name] [contact].

If found eligible for the study and agree to consent to participate, subjects will be matched based on disability level (EDSS), and randomized to either conventional physical therapy (CPT) group or CPT with G-EO training using a random numbers generator and concealed allocation.

4.0 Study Procedures

Screening

Potential subjects will be referred to the study via IU Health Physicians who specialize in the treatment and management of individuals with Multiple Sclerosis. A member of the research team will screen the referral by contacting the physician and confirming they meet the necessary inclusion and exclusion criteria. Following confirmation of criteria, potential subjects will be contacted by phone to schedule an initial visit for consent and assessment of baseline data.

Assessments

The study outcomes will be collected by treatment-blinded researchers. All participants on Day 1 who consent to be in the study will complete the following mobility outcomes:

1. Spatial and temporal gait kinematics will be assessed using a PKMAS Zeno Walkway (Protokinetics). Participants will be asked to walk over a 14 foot pressure mat that will capture their gait kinematics and speed.
2. A 2-minute walk (2MWT) tests to determine walking endurance. Subjects will be asked to walk for 2 minutes along a 30m track. Subjects may stop and rest as often as needed.
3. Balance assessment using the Neurocom Balance Master. Subjects will be asked to stand on a balance platform while the load cells in the force-plate measures postural stability when challenged. All subjects will be in a safety harness to prevent falling.
4. Their level of perceived fatigue using the Modified Fatigue Impact Scale. They will complete a questionnaire.
5. Their level of depression using the Hospital Anxiety and Depression Scale. They will complete a questionnaire.
6. Their level of pain assessed by the McGill Pain Questionnaire. They will complete a questionnaire.
7. Their level of health-related quality of life assessed by the Multiple Sclerosis Impact Scale-29. They will complete a questionnaire.
8. Their perceived ability to perform Activities of Daily Living (ADL) using the Late-Life Function and Disability Inventory. They will complete a questionnaire.

Participants who complete the first 6 weeks of training will be asked to complete assessments 1 thru 3. Participants who complete all 12 weeks of training will be asked to complete all assessments one final time.

Schedule

Following completion of day 1 assessments, all subjects will be scheduled for the intervention phase of the study. Regardless of group allocation, each participant will receive 20 total visits scheduled ideally for two times a week for 10 weeks. Following the completion of the first 10 treatments, all subjects will be asked to complete assessments #1 thru #3 above. Following completion of the additional 10 treatments (total of 20 treatment sessions), each subject will complete all assessments performed on Day 1. (See Table 1) If a subject cancels a treatment session, it will be rescheduled to ensure that all subjects complete the total of 20 treatment sessions prior to final testing. If a subject misses three consecutive treatment sessions, they will be dropped from the study due to inconsistency in treatment carryover. Cancellations and changes in patient scheduling represents a true clinical environment and represents normal clinical patient management. Therefore, the emphasis is on total number of treatments (20) and not on total number of weeks.

Table 1. Summary Clinical Trials (14-week span) Procedures with Human Subjects.

Pre-Intervention Phase		Intervention Phase	Mid Intervention Phase	Intervention Phase	Post Intervention
Day 1	Day 1 Measurement	6 weeks intervention period	Mid Treatment Assessment	6 weeks intervention period	Post Assessment

 • Screening of Inclusion • Informed consent obtained • Disability match and random assignment to CPT or GEO 	Outcome Measurement 
 1. Comfortable Walking Speed/Mechanics Trial 1 (14') 2. Trial 2 (14') 3. Trial 3 (14') 2. Walking Endurance 2 MWT 3. Balance Neurocom 4. Fatigue Modified Fatigue Impact Scale 5. Depression Hospital Anxiety and Depression Scale 6. Pain McGill Pain Questionnaire 7. Quality of Life MS Impact Scale 8. ADLs 	Treatment and control group 2x a week	Outcome Measurement 
 1. Comfortable Walking Speed/Mechanics Trial 1 (14') 2. Trial 2 (14') 3. Trial 3 (14') 2. Walking Endurance 2 MWT 3. Balance Neurocom 	Treatment and control group 2x a week	Outcome Measurement 
 1. Comfortable Walking Speed/Mechanics Trial 1 (14') 2. Trial 2 (14') 3. Trial 3 (14') 2. Walking Endurance 2 MWT 3. Balance Neurocom 4. Fatigue Modified Fatigue Impact Scale 5. Depression Hospital Anxiety and Depression Scale 6. Pain McGill Pain Questionnaire 7. Quality of Life MS Impact

	Late Life Function and Disability Inventory				Scale 8. ADLs Late Life Function and Disability Inventory
--	---	--	--	--	---

Intervention

The intervention will be delivered through the Neurorehabilitation and Robotics Clinic by three trained Physical Therapists with oversight from [name]. The clinicians involved in the delivery of the intervention will not be involved in outcome assessments. Participants in both conditions will receive conventional physical therapy (CPT) as usual care. Participants in the G-EO training condition will also receive robot-assisted gait training. This design will control for attention and social contact, total rehabilitation time, and intensity. Both conditions will be delivered at the same frequency (2x/week), intensity (40 to 60 minutes), and duration over 12-weeks. Progression will occur by increasing the session intensity weekly. Training intensity will be monitored and standardized using the Borg Rating of Perceived Exertion³⁸ scale, and will progress from 'fairly light' (11) to 'somewhat hard' (13). This prescription is consistent and appropriate for individuals with progressive MS with mobility impairment and low fitness levels. Progression will occur by increasing the session duration by ~5min/week up to 60 minutes per session. Total training time includes both CPT and G-EO training for the G-EO condition (i.e., 30min of CPT + 30min G-EO). Training sessions will not exceed 60 minutes. We will record all training parameters. Physical therapy training sessions will involve: 3-5 minute warm-up, stretching, progressive strength training exercises, and gait and balance training. Additional strategies for home exercises, energy conservation, fall prevention, and appropriate assistive devices (i.e., orthotics) will be provided universally.

Conventional physical therapy (CPT): A CPT session will involve a 3-5 minute warm-up, stretching, progressive strength training exercises, and gait and balance training.

G-EO training: Using the G-EO System, participants will be secured with the appropriate sized harness and attached to an overhead body-weight support system, with feet secured to pressure sensitive footplates. Each session will begin with a 3-5 minute warm-up in the continuous passive mode (cadence ~40-45 steps/minute). The participant will then be transitioned into the adaptive training phase for practicing repetitive floor walking for up to 30 minutes. During this phase, the force produced by the robot is modulated to support the effort of the patient in producing a typical walking pattern.

Feasibility and Safety

Feasibility outcomes will involve process, resources, management, and scientific assessment. Process metrics will include recruitment, retention, and adherence rates assessed by the movement of participants through each stage of the study and training data. Resource metrics will include evaluation of the equipment and facilities through feedback from the therapists. Time to completion relative to proposed target dates will also be reviewed. Management metrics will include data management, documentation of patient progress, record of adverse events, and

National MS Society, , <http://nationalmssociety.org/for-professionals/researchers/index.aspx>

compliance with approved protocols. Safety will be evaluated through assessment of recorded adverse events.

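### Three consecutive missed sessions end study participation, not only training, so the outcome of a harm that kept someone away, and any later event, may not reach the safety comparison

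*Combined protocol and SAP*

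**What the plan says.** The removal rule is in section 4.0, Schedule: "If a subject misses three consecutive treatment sessions, they will be dropped from the study due to inconsistency in treatment carryover". The sentence before it covers cancellations: "If a subject cancels a treatment session, it will be rescheduled to ensure that all subjects complete the total of 20 treatment sessions". The text after it treats cancellations as an ordinary part of clinical practice and concludes: "Therefore, the emphasis is on total number of treatments (20) and not on total number of weeks". Neither missing nor cancelling is defined, and no exception for illness, injury or an adverse event is stated.

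On timing, the same section says that "each participant will receive 20 total visits scheduled ideally for two times a week for 10 weeks". After Day 1, the planned contacts are the training visits and two assessments, and both assessments depend on training having been done. Section 4.0, Assessments, says "Participants who complete the first 6 weeks of training will be asked to complete assessments 1 thru 3" and "Participants who complete all 12 weeks of training will be asked to complete all assessments one final time".

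On safety, section 4.0, Feasibility and Safety, says "Management metrics will include data management, documentation of patient progress, record of adverse events, and", and the sentence goes on to protocol compliance. It then says "Safety will be evaluated through assessment of recorded adverse events". Retention is listed there as a process metric. Section 1.0 makes safety part of Aim 1, and section 5.0 compares safety between groups with chi-square tests and independent-samples t-tests.

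**The concern.** The rule gives a training reason for a study-level consequence. Poor carryover may justify ending the sessions. It does not justify ending observation of a person whose absence may itself be a sign of harm. In a progressive MS population with EDSS 4.0 to 7.5, an absence of a week and a half for a medical reason is plausible.

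If such an absence counts as missed, the people whose observation ends early would include those kept away by harm. Their triggering event could enter the between-group comparison. Its course, its resolution and anything that happens later have no stated route into the data. The text also does not say whether the reason for an exit is recorded. Without it, retention could not be split into exits due to harm and exits due to scheduling in each arm.

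This point concerns the safety record. The loss of the efficacy assessments for the same people is a separate matter.

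**Working it through.** The plan gives no figure of its own on this point, so there is nothing to reproduce. The check has two parts.

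**1. The text, side by side**

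- *Consequence:* leaving the study, not only the sessions (Schedule).
- *Exception for harm:* none stated.
- *Cancelled or missed:* the two words have different consequences, rescheduling against counting towards removal. The text does not say which applies to someone absent for three sessions with an injury or a relapse.
- *Contact after removal:* none scheduled. The remaining contacts are training visits, which have ended, and assessments tied to completed training.
- *Recording of the trigger:* possible, because adverse events and patient progress are documented (Feasibility and Safety).

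**2. How much observation is at stake**

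Inputs from the documents: 20 visits, two a week, 10 weeks (Schedule), and 20 participants in two groups (section 3.0).

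Assumptions: 10 per arm, since the allocation ratio is not stated; missed slots are not made up; and the comparison is with a completer at the same pace. Weeks 6 and 12 appear elsewhere in section 4.0, but 20 visits at two a week take 10 weeks, so the arithmetic uses 10.

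Time to trigger: 3 / 2 = 1.5 weeks.

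For a participant who attended k sessions and then missed three:

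- exit week = (k + 3) / 2
- weeks lost = 10 − (k + 3) / 2
- training visits lost = 20 − 3 − k = 17 − k
- assessments lost = 2 if k < 10, otherwise 1
- share of the arm's planned time = weeks lost / (10 × 10) participant-weeks

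| k attended | Exit week | Weeks lost | Visits lost | Assessments lost | Share of arm |
|---|---|---|---|---|---|
| 0 | 1.5 | 8.5 | 17 | 2 | 8.5% |
| 1 | 2.0 | 8.0 | 16 | 2 | 8.0% |
| 7 | 5.0 | 5.0 | 10 | 2 | 5.0% |
| 10 | 6.5 | 3.5 | 7 | 1 | 3.5% |
| 17 | 10.0 | 0 | 0 | 1 | 0% |

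One removal therefore costs an arm 0% to 8.5% of its planned participant-weeks, and two cost 0% to 17% (2 × 8.5%). For the person concerned the loss can reach 8.5 / 10 = 85% of the planned weeks.

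Whether the rule will be used at all is unknown. If each participant had probability p of being removed under it, the chance of at least one removal among 20 is 1 − (1 − p)^20. For assumed p of 2%, 5%, 10% and 20% this gives 33%, 64%, 88% and 99%. These figures cover removals for any reason, and the conclusion does not depend on them.

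**The case against.** The strongest reply is that the Schedule already protects most medical absences. A participant who telephones to say they are unwell has, on a natural reading, cancelled. Cancelled sessions are rescheduled, and the emphasis is on 20 treatments, not on weeks. On that reading the rule reaches a medical absence only when nobody was told. This is a fair reading and it narrows the concern, but the text does not secure it, because the boundary is left undefined. It would be wrong to say that the plan makes no distinction between the two words. It gives them different consequences and leaves the dividing line open.

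A second reply is that the harm sequence is conditional: a harm, three sessions lost, the absence classed as missed, and then no follow-up. That stands, and it is why the consequence is stated as something that may happen.

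A third is that the triggering event can already count in the comparison, and that event course is not named as a compared outcome. That also stands. What could be missing from the comparison is later events. The outcome of the first event could be missing from the safety description.

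A reader might infer more than the documents support:

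- *That the triggering harm goes unrecorded.* Adverse events and patient progress are to be documented.
- *That follow-up of an open event stops.* The text says neither that it stops nor that it continues, and any withdrawal terms in the removed consent pages cannot be seen.
- *That reasons for exit are not kept.* Silence on a reason field does not show this.
- *That the comparison favours the G-EO arm.* The rule applies to both arms, and nothing indicates a direction.
- *That wide intervals show the damage.* With 10 per arm, 0/10 has an exact 95% interval of 0% to 30.8%. That width reflects the small sample, not this rule.

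**Conclusion.** The concern holds in a limited form. The rule as written ends study participation for a reason that supports only ending training. It has no stated exception for harm, and the visible protocol schedules no contact afterwards. Because the line between a missed and a cancelled session is undefined, a medical absence of about 1.5 weeks could trigger it, and the outcome of the event and any later event may not reach the Aim 1 safety comparison.

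The effect on an arm is modest: 0% to 8.5% of planned participant-weeks for one removal and 0% to 17% for two. This rests on the 10-week schedule, an assumed 10 per arm and missed slots not made up. The loss matters more than its size suggests because it could fall on the participants whose safety information is most relevant. It is not fatal to the trial. The change is worth making because safety is a stated aim and the remedy is cheap. Confidence is medium, since the consent pages are not available.

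**What to change.** Four changes to section 4.0:

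1. In the removal rule, make the consequence stopping study training instead of leaving the study.
2. State that an absence for an adverse event or MS worsening is handled as a cancellation, and define a missed session accordingly.
3. Keep anyone who stops training in adverse-event follow-up by telephone until their planned final-assessment date, and follow open events to resolution.
4. Record the reason for stopping (adverse event or MS worsening, scheduling, other), and report stops due to adverse events by arm, separately from retention.

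The carryover rule stays in force for training. The cost is a wording change, one data field and a few calls to those who stop early. The safety record may look slightly less favourable. A fixed call window over the 14-week span in Table 1 for completers is not needed for this fix: at two sessions a week completers finish at week 10, so it could mean calls to all 20 participants. If the team already intends this follow-up, the change only writes it down.

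### Table 1 places random assignment before the Day 1 outcome measurement, and no other visible text requires baseline to be completed first

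*Combined protocol and SAP*

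**What the plan says.** Table 1 (Section 4.0, Study Procedures) is captioned as a summary of procedures. Its first column, headed Day 1, lists screening, then informed consent, then "Disability match and random assignment to CPT or GEO". The next column is the Day 1 measurement, with all eight outcome measures.

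The prose touches the order in several places:

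- Section 3.0: "Consent will be obtained before randomization and assessments". Later in the same section: "If found eligible for the study and agree to consent to participate, subjects will be matched based on disability level (EDSS), and randomized".
- Section 4.0, Screening: the referral is checked with the physician first, and the person is then phoned to "schedule an initial visit for consent and assessment of baseline data".
- Section 4.0, Assessments: "All participants on Day 1 who consent to be in the study will complete the following mobility outcomes".
- Section 4.0, Schedule: "Following completion of day 1 assessments, all subjects will be scheduled for the intervention phase of the study".

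On blinding, Section 1.0 calls the trial single-blinded, and Section 4.0 says: "The study outcomes will be collected by treatment-blinded researchers". Section 3.0 also specifies concealed allocation.

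**The concern.** Baseline is best collected before anyone can know the assignment, because a Day 1 value taken then cannot have been influenced by it. The only visible place that sets randomization and baseline in an order puts randomization first.

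The measures most open to such influence are those that participants rate themselves: fatigue, depression, pain, quality of life and activities of daily living (items 4 to 8). A participant who has just learned that the robotic training is, or is not, part of the allocation might answer differently. A group difference on Day 1 would then mix chance with reaction to the assignment, and with 20 participants the two could hardly be told apart. The affected value would pass into the Aim 2 analysis. Aim 1 (safety and feasibility) is not involved.

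**Working it through.** The plan gives no figure to reproduce, since the issue is the order of procedures. The check sets the texts side by side.

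**1. What each text requires before randomization, and what baseline must precede.**

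| Place | What it fixes | Baseline required before randomization? |
|---|---|---|
| Section 3.0, consent sentence | Consent precedes both randomization and assessments; those two are not ordered | No |
| Section 3.0, randomization sentence | Randomization follows eligibility and consent | No |
| Section 4.0, Screening | The initial visit covers consent and baseline; randomization is not mentioned | No |
| Section 4.0, Assessments | Day 1 measures follow consent | No |
| Section 4.0, Schedule | Day 1 measures precede scheduling of the intervention phase | No; only before treatment is scheduled |
| Table 1 | Assignment is listed before the Day 1 measurement | No; the opposite order is shown |

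Every line of prose is compatible with baseline first. None requires it.

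**2. Could staff follow the Table 1 order?** Yes. Matching uses the EDSS. The EDSS range is an inclusion criterion (Section 2.0), and criteria are confirmed with the physician before the visit. The EDSS is not among the eight Day 1 measures, so nothing in the stated workflow makes assignment wait for them.

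**3. Do the stated safeguards cover the gap?** Concealed allocation protects the assignment until it is made; it sets no time for telling the participant. Blinded outcome collectors, and treating therapists who take no part in assessment, guard against assessor bias. Neither blinds the participant, who is the rater for items 4 to 8.

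**4. Which outcomes are exposed?** Items 1 to 3 are measured three times (Day 1, mid, post). Items 4 to 8 are measured twice (Day 1, post). That makes 5 of 8 instruments that are self-completed and have only these two time points.

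**5. Does the Day 1 value enter the analysis?** Section 5.0 specifies two levels of Time without naming them. For items 4 to 8 only two measurements exist, so Day 1 must be one of them. The Group by Time contrast is then

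(post, G-EO − Day 1, G-EO) − (post, CPT − Day 1, CPT).

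A between-arm shift in the Day 1 value enters this contrast directly, with a minus sign. For items 1 to 3 the use of Day 1 is likely but not stated.

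**6. How large could the shift be?** The documents give no figure from which to estimate its size or direction.

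**The case against.** The strongest case against is that this is a wording matter. Table 1 is a summary, and its first column is not a strict record of Day 1: it includes screening, whereas the Screening text has the research team do this beforehand ("A member of the research team will screen the referral by contacting the physician"). The prose leans toward baseline first, since the initial visit is described as consent plus baseline and group allocation is mentioned only after the Day 1 assessments. The table shows assignment, not disclosure. Consent pages were removed before review and might say when participants are told.

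Much of this stands. A reader might infer from Table 1 that participants will know their arm when they fill in the baseline questionnaires. The documents do not support that: it needs both the table's order in practice and disclosure at assignment, and the visible text establishes neither. The silence on disclosure is therefore only a condition of the concern here, not a fault in its own right.

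A reader might also infer that baseline-first order would remove or always reduce bias in the Group by Time contrast. That does not follow. Participants are not described as blinded at the post assessment, and a reaction to the assignment that is equal at both times would cancel in the contrast. What baseline-first order does secure is a Day 1 value that the assignment cannot have touched.

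The objection does not remove the main point: the only text that orders the two steps puts randomization first, and no visible sentence overrides it.

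**Conclusion.** The point holds as a minor one: a cheap improvement to the design. Following the plan's only stated order would allow a post-assignment baseline for 5 of the 8 instruments, and for those five the Day 1 value necessarily enters the Aim 2 ANOVA. The consequence rests on two assumptions: that Table 1 is followed as listed, and that the arm is known at assignment. The risk is avoidable, of unknown size and direction, and confined to Aim 2. It is not evidence that the baseline data are biased.

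**What to change.** In Table 1, move the entry for disability matching and random assignment to after the Day 1 measurement. In Section 3.0, add a sentence saying that the allocation is opened, and disclosed to the participant, only after all Day 1 assessments are complete. If this is already the practice, the change merely records it.

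The cost is one table entry, a sentence or so, and a small change in Day 1 workflow. The EDSS score for matching must be in hand by the end of the Day 1 measures. The documents do not say whether matching also needs another enrolled participant. If it does not, assignment can still take place on Day 1 without an extra visit; if it does, the workflow must allow for a later assignment.
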